### 13.8.2 Secondary Endpoints

The following are defined as secondary endpoints:

- Proportion of subjects with complete remission or partial remission of proteinuria at Weeks 8 and 12
- Proportion of subjects with complete remission of proteinuria at Weeks 8, 12, and 24
- Proportion of subjects with UPCR  $<0.5$  mg/mg at Weeks 8, 12, and 24
- Proportion of subjects with partial remission of proteinuria at Weeks 8, 12, and 24
- Time to first occurrence of complete or partial remission of proteinuria
- Time to first occurrence of complete remission of proteinuria

- Time to first occurrence of partial remission of proteinuria
- Time to first occurrence of 50% reduction in UPCR from baseline
- Duration of UPCR <0.3 mg/mg
- Change from baseline in UPCR at each time point
- Proportion of subjects with a confirmed >30% decrease from baseline in eGFR (utilizing the CKD-EPI formula) at each time point (Baseline eGFR is defined as the last assessment prior to first dose of study treatment)
- Proportion of subjects with a confirmed >30% increase in eGFR from the final visit (Week 24 or last on-treatment visit, for subjects who discontinue prematurely) to the second Safety Follow-up visit (Visit 10)
- Change in UPCR from the final visit (Week 24 or last on-treatment visit, for subjects who discontinue prematurely) to the second Safety Follow-up visit (Visit 10)
- Change in eGFR from the final visit (Week 24 or last on-treatment visit, for subjects who discontinue prematurely) to the second Safety Follow-up visit (Visit 10)
- Change from baseline in serum creatinine, serum albumin, and eGFR at each time point
- QoL assessments
  - Mean change in PROMIS measures at Week 24
  - Change from baseline in KDQOL-SF™ score at Week 24
- Safety and tolerability over 24 weeks
- Renal biopsy: descriptive analyses of changes in histopathology will be evaluated in post-treatment (24 weeks) renal biopsies in a subset of patients
- Change from baseline to Week 4 and 24 in the following biomarkers:
  - Urine nephrin
  - Urine synaptopodin
  - Serum TGF-β

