-------------	---

Procedures (cont'd)	
Doses and dose increments smaller than anticipated may be proposed for Cohort 2 based on the safety and tolerability results from the Cohort 1.
 
All subjects will complete dosing through 24 weeks of study treatment and will have 2 Safety Follow-Up visits, 1 and 2 weeks after completion of treatment (i.e., at Week 25 and Week 26). Subjects who permanently discontinue study treatment before the Week 24 visit will return for all remaining study visits and assessments, including the 2 Safety Follow-Up visits, unless they have withdrawn consent.

Sample Size:	
As this is an exploratory study, sample size calculations are not required. It is estimated that approximately 20 subjects will be recruited, with up to 10 subjects in Cohort 1 and at least 10 subjects in Cohort 2.

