## **5.6 Discontinuation of Study Treatment**

Discontinuation of study treatment does not necessarily constitute withdrawal from the study.

If any subject is discontinued from study treatment, the reason for discontinuation will be documented in the eCRF. If the reason for discontinuing study treatment is an AE or an abnormal laboratory test result, the specific event or test will be recorded in the eCRF.

If possible, subjects who are permanently discontinued from study treatment before the Week 24 visit should undergo all study assessments up to and including the Week 24 (or Early Termination Visit – Visit 8) and Safety Follow-up visits where appropriate. All subjects that discontinue study treatment should attend at least 2 further assessments after the last dose of study drug.

Guidance on when study treatment must be discontinued is in [Section 7.4, Voclosporin Dose Modification](#).

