### **13.4 Datasets**

Assessments taken at each visit will be analyzed using 2 different datasets. The first will be the observed cases dataset whereby all values collected will contribute to the dataset. A second dataset will be used for summaries and analyses incorporating data carried forward from a subject's last known value. This dataset will be referred to as the last observation carried forward dataset and as such, all subjects with any post-baseline efficacy assessment will contribute to the Week 24 analyses.

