### **13.9 Statistical and Analytical Methods**

All statistical analyses relating to the primary and secondary objectives will be undertaken at study closure and will incorporate all available data.

In order to aid dose decisions for Cohort 2, an analysis of the first 5 or 6 subjects in Cohort 1 will be undertaken once the 5th or 6th subject reaches Week 12.

Given the small sample size, all analyses will be descriptive in nature.

Binary remission endpoints will be summarized using counts and proportions while continuous data will be summarized using means, SDs, medians, minimums and maximums. Kaplan-Meier methodology will be used for the analysis of time-to endpoints. Confidence intervals for proportions may be calculated but it is recognized that such intervals, being based on 20 patients, will be very wide. As an example, the 95% Clopper-Pearson CI for a proportion of 30% based on 20 patients is (11.9%, 54.3%).

The analysis of the primary endpoint, complete or partial remission of proteinuria at Week 24, will be conducted on the ITT set and confirmed with the PPS (if applicable). Remission of proteinuria will be summarized and an exact 2-sided 95% CI for the remission rate will be calculated.

The analyses of the secondary endpoints will incorporate the use of 2-sided 95% CIs and are described below:

- Binary endpoints will be summarized using counts and proportions along with exact 2-sided 95% CIs.
- Endpoints measured as a time-to-event will be displayed using Kaplan-Meier methodology. Median time-to-event along with 2-sided 95% CIs will be displayed.
- Other endpoints will be summarized by visit. Absolute values and differences between baseline and each time point up to and including Week 24 will be summarized using means and 2-sided 95% CIs. Changes between last on treatment value and post treatment follow-up will also be summarized.

Given the nature of the study, additional exploratory analysis will be undertaken as appropriate. This may include the reporting of individual case studies.

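### Week 24 mean change in eGFR and creatinine pools on-drug values with values taken after a permanent stop; a change to the last on-treatment value should be added in the SAP (minor)

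*Combined protocol and SAP*

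**What the plan says.** **Endpoint and summary.** Section 13.8.2 lists "Change from baseline in serum creatinine, serum albumin, and eGFR at each time point". Section 13.9 summarises such endpoints by visit up to Week 24, with means and 95% CIs. Section 13.10 treats safety laboratory values the same way. None of these limits the values to subjects still on drug.

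**Attendance after a stop.** The Synopsis states: "Subjects who permanently discontinue study treatment before the Week 24 visit will return for all remaining study visits and assessments". Section 5.6 is softer. If possible, these subjects "should undergo all study assessments up to and including the Week 24" visit.

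**Datasets (Section 13.4).** In the observed-cases dataset, "all values collected will contribute to the dataset". The second dataset carries forward the "last known value. This dataset will be referred to as the last observation carried forward dataset". Neither definition mentions whether the subject was on drug.

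**Where the on-drug distinction is used.** Section 13.8.2 defines a final visit ("Week 24 or last on-treatment visit, for subjects who discontinue prematurely") as the starting point for changes to Visit 10. Section 13.9 adds: "Changes between last on treatment value and post treatment follow-up will also be summarized". Section 13.10 also limits treatment-emergent adverse events to 14 days after the last dose. No change from baseline ends at the last on-treatment value.

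**Related output.** Section 13.8.2 also has "Proportion of subjects with a confirmed >30% decrease from baseline in eGFR", counted at each time point.

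**The concern.** Safety and tolerability is the secondary objective (Section 3.2). Section 1.2.4 names renal dysfunction as a known toxicity of the class, and Section 2.1 describes the risk as dose-related and reversible. If it is reversible, a value taken weeks after the drug was stopped says little about the fall on drug. A subject stopped for a 35% fall who has recovered by Week 24 enters the Week 24 mean as unchanged from baseline.

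LOCF does not restore the on-drug value. For a subject who stops and keeps attending, the last known value is itself off drug. The rebound after stopping has its own summary, while the matching fall from baseline has none. At stake is how a reader of the final report interprets the mean renal change on voclosporin.

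**Working it through.** **The plan's own figure.** The only computed figure in Section 13.9 is the exact CI for 30% of 20 patients. For 6/20 the Clopper-Pearson limits are 11.89% and 54.28%, matching the stated (11.9%, 54.3%). It does not bear on this point, but it confirms the interval method used in step 4.

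**1. How many stops to expect.** Section 1.2.4 gives permanent stops for decreased GFR in lupus nephritis of 7.9% (23.7 mg BID) and 5.7% (39.5 mg BID). Applying these rates here is an assumption. They may be high for 24 weeks, since Section 2.1 cites Week 48 results for a lupus nephritis study; stops for other reasons would add to them.

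| n | rate | expected stops | P(at least 1) | P(at least 2) |
|---|---|---|---|---|
| 20 | 7.9% | 1.58 | 81% | 48% |
| 20 | 5.7% | 1.14 | 69% | 32% |
| 10 | 7.9% | 0.79 | 56% | 18% |
| 10 | 5.7% | 0.57 | 44% | 11% |

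**2. Size of the shift.** Assumed inputs, none from the documents: an eGFR fall of 5% in subjects who stay on drug, a 35% fall at the last on-drug value in the k subjects stopped for it, and a share r of that fall recovered by Week 24.

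- Mean fall to last on-drug value = [35k + 5(n − k)] / n
- All-values Week 24 mean fall = [35k(1 − r) + 5(n − k)] / n
- Gap = 35kr / n, which does not depend on the 5%

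| n, k | last on-drug mean | Week 24 mean, r = 1 | r = 0.5 | gap, r = 1 | gap, r = 0.5 |
|---|---|---|---|---|---|
| 20, 2 | 8.0% | 4.5% | 6.25% | 3.5 | 1.75 |
| 20, 1 | 6.5% | 4.75% | 5.625% | 1.75 | 0.875 |
| 10, 1 | 8.0% | 4.5% | 6.25% | 3.5 | 1.75 |

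With n = 20, k = 2 and r = 0.3, the Week 24 mean is 6.95% and the gap 1.05 points. With no recovery the gap is zero.

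**3. Scale against the CI.** Half-width = t(0.975, n − 1) × √[(between-group variance + within-group SD²) / n]. For n = 20 and k = 2, the between-group variance is (2 × 27² + 18 × 3²) / 19 = 85.3 (SD 9.23). The half-width is 4.3 points with no other spread, 6.4 if the within-group SD is 10 points and 8.2 if it is 15. The minimum half-width is 3.1 points for n = 20, k = 1 and 6.8 for n = 10, k = 1. Every gap above is inside its interval. Two stops in a cohort of 10 with full recovery would give 7.0 points, against a half-width of at least 9.0, but the chance of two such stops is only 11% to 18% at the rates in step 1.

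**4. What the categorical endpoint shows.** Two of 20 subjects with a confirmed fall above 30% at the same visit read 10% (exact 95% CI 1.2% to 31.7%). If they fall at different visits and have recovered by the next, each visit reads 5% (0.1% to 24.9%). At Week 24, after recovery off drug, it reads 0% (0% to 16.8%).

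**5. The direction can reverse.** Section 7.4.1 allows a stop for non-response. Suppose 2 of 20 stop at a 5% fall and are 20% down by Week 24. The all-values mean is (2 × 20 + 18 × 5) / 20 = 6.5%, against 5.0% to the last on-drug value, an overstatement of 1.5 points.

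**The case against.** **The all-values table is legitimate.** Efficacy analyses use the ITT set and all available data, so keeping values after a stop answers the treatment-policy question. This stands: the table is not an error, and the point is that it should not be alone.

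**The SAP may already contain this.** Section 13.1 calls itself a general description and defers full detail to the SAP, as does Section 13.10. No separate SAP text is in the document reviewed. A reader might infer that the trial will never report an on-drug renal change; the documents do not support that. The point concerns the rules Section 13 does state.

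**The harm is not hidden.** A reader might infer that the plan conceals renal toxicity. It does not. A fall found at a scheduled visit enters that visit's mean and minimum. The plan also reports the confirmed decrease above 30%, discontinuations, adverse events, the change to Visit 10 and possibly individual case studies. These show part of the harm, but none gives the mean fall from baseline to the end of treatment.

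**Few subjects may be affected.** Section 7.4.2 manages falls by holding, retesting, reducing and restarting, and sets no automatic permanent renal stop. Short holds matter little, because the retest is within 48 hours. Subjects who leave the study have Visit 8 at withdrawal, often close to the last dose. Attendance after a stop is only if possible in Section 5.6. All of this stands and keeps the point minor.

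**On-drug summaries have their own bias.** Section 7.4.2 warns of wide creatinine fluctuations, so a value that prompts a stop will partly regress to the mean. Under Section 7.4.2.1 drug is interrupted before the retest, so the confirming value is not strictly on drug. A worst on-treatment value is a minimum over repeated draws, with extra draws triggered by falls and no control arm for calibration. These objections shape the fix but do not remove the need for it.

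**Conclusion.** The point holds as a minor, inexpensive improvement. Under the stated rules, mean change in eGFR and creatinine at later visits pools on-drug values with values taken after a permanent stop in both datasets, and the last on-treatment anchor never closes a change from baseline. The likely effect is to understate the on-drug fall when stops are for a reversible eGFR decrease; the reverse is possible when non-responders decline off drug.

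The size is about 1 to 3.5 percentage points for one or two stops in 20 subjects or one in 10. It rests on the assumed 35% fall and recovery share, on stop rates borrowed from lupus nephritis, and on stopped subjects continuing to attend. It is within the CI.

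A reader might infer that the efficacy conclusion or dose selection is compromised. Neither is: the primary endpoint uses UPCR only, and the Cohort 2 decision is a review of the first 5 or 6 subjects at Week 12 whose eGFR guidance counts subjects, not means. Results are descriptive and hypothesis-generating (Section 13.2). The consequence is confined to how the final mean renal change is read.

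**What to change.** Keep the all-values by-visit table. In the SAP, for eGFR and serum creatinine, overall and by cohort:

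- Add change from baseline to the last on-treatment value, defined as the last central laboratory value taken on or before the last dose (Week 24 if still on drug). When drug was held before the confirming retest, show the retest beside it.
- In the LOCF dataset, do not carry forward values taken after a permanent stop for these two measures.
- Treat a worst on-treatment value as optional. If shown, label it as biased downward by repeated and unscheduled draws.

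An on-treatment by-visit mean is not a substitute, because subjects stopped for an eGFR fall leave it. In the step 2 example it reads 5.0% at Week 24 for every row.

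The cost is SAP wording and a few extra tables from dosing dates and laboratory results already collected. The stated fall may look slightly less favourable, and the last on-drug value carries some regression to the mean. If the SAP already has this output, nothing changes.

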### **13.9 Statistical and Analytical Methods**

All statistical analyses relating to the primary and secondary objectives will be undertaken at study closure and will incorporate all available data.

In order to aid dose decisions for Cohort 2, an analysis of the first 5 or 6 subjects in Cohort 1 will be undertaken once the 5th or 6th subject reaches Week 12.

Given the small sample size, all analyses will be descriptive in nature.

Binary remission endpoints will be summarized using counts and proportions while continuous data will be summarized using means, SDs, medians, minimums and maximums. Kaplan-Meier methodology will be used for the analysis of time-to endpoints. Confidence intervals for proportions may be calculated but it is recognized that such intervals, being based on 20 patients, will be very wide. As an example, the 95% Clopper-Pearson CI for a proportion of 30% based on 20 patients is (11.9%, 54.3%).

The analysis of the primary endpoint, complete or partial remission of proteinuria at Week 24, will be conducted on the ITT set and confirmed with the PPS (if applicable). Remission of proteinuria will be summarized and an exact 2-sided 95% CI for the remission rate will be calculated.

The analyses of the secondary endpoints will incorporate the use of 2-sided 95% CIs and are described below:

- Binary endpoints will be summarized using counts and proportions along with exact 2-sided 95% CIs.
- Endpoints measured as a time-to-event will be displayed using Kaplan-Meier methodology. Median time-to-event along with 2-sided 95% CIs will be displayed.
- Other endpoints will be summarized by visit. Absolute values and differences between baseline and each time point up to and including Week 24 will be summarized using means and 2-sided 95% CIs. Changes between last on treatment value and post treatment follow-up will also be summarized.

Given the nature of the study, additional exploratory analysis will be undertaken as appropriate. This may include the reporting of individual case studies.

### **13.10 Safety Evaluations**

Specific safety endpoints are as follows:

- Biochemical (including liver function tests) and hematological laboratory tests

- AE profile and routine biochemical and hematological safety parameters
- Vital signs (BP, HR, temperature) at specific time points and change from baseline
- Standard 12-lead ECGs change from baseline
- Discontinuations from treatment
- Concomitant medications

Laboratory values, vital signs, and other safety parameters providing numeric data will be summarized by visit, and as change from baseline.

Adverse events and diseases will be coded using the latest available version of the Medical Dictionary for Regulatory Activities, the version of which will be provided in the clinical study report.

Treatment-emergent adverse events will be summarized by treatment arm, System Organ Class, and Preferred Term. SAEs, SAEs that led to death, and SAEs/AEs that led to withdrawal will also be summarized and listed.

Only AEs which started on or after the date of first dose of study treatment and up until 14 days after last dose will be considered TEAEs, though all AEs after informed consent will be recorded. SAEs occurring at any time after informed consent and prior to first study medication will be listed.

All prior and concomitant medications will be summarized using preferred terms and ATC Level 2.

Details of these and other analyses will be provided in the SAP.

All study data analyses involving laboratory values will be based on results from the central laboratory.

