- 4 BP, pulse, temperature, weight, and height. Height included at initial screening assessment only. At stability assessments, BP only will be included.
- 5 In the event that a subject is noted to have a QTcF value exceeding 500 msec, or an increase of  $>60$  msec from baseline, the ECG should be repeated within 24 hours. Further details provided in the study protocol.
- 6 Laboratory assessments will be performed according to the schedule in the study protocol. Subjects must be fasting for at least 8-12 hours at Baseline and at end of study/early termination visit.
- 7 Pharmacokinetic assessments will be done at Weeks 4 and 24. PK samples will be drawn prior to study treatment dosing (trough sample), and at 1, 2 and 4 hours post-dose. In the event a subject experiences an SAE or requires a dose modification or is withdrawn from treatment, a voclosporin sample should be taken, with a trough sample preferred.
- 8 The UPCR will be calculated both from the FMV and from standard urinalysis results. If the FMV is for some reason not available, then standard urinalysis from a 24-hour urine collection may be substituted as an exception but only after agreement is reached with the Medical Monitor.
- 9 24-hour urine collection should begin 2 days prior to the scheduled study visit in order not to coincide with the FMV sampling due on the day of the study visit.
- 10 Patient Reported Outcome Measurement Information system (PROMIS) and Kidney Disease Quality of Life-Short Form (KDQOL-SFTM).
- 11 Serum pregnancy test to be evaluated at central laboratory at Screening and Week 24; urine pregnancy test will be performed locally at all other visits as applicable.
- 12 If screening visit occurs on the same day as informed consent, any findings are to be recorded as Medical History. Any change since the date of signed consent and/or during the screening period would be considered an AE.
- 13 Subjects in Cohort 1, will be contacted by telephone at the end of Week 1 as a reminder to increase their dose to 2 capsules (15.8 mg) BID for 1 week, starting at Week 2. Subjects will be contacted again by telephone at the end of Week 2 as a reminder to increase their dose to 3 capsules (23.7 mg) BID, starting at Week 3, for the remainder of the treatment period. Subjects in Cohort 2, will also be contacted at the end of each week (as required) up to Week 4, as a reminder to increase their dose to the maximum selected for Cohort 2.
- 14 Compliance only.

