### **10.2 Adverse Event Descriptors**

#### **10.2.1 Intensity/Severity Categorization**

The term "severe" is often used to describe the intensity (severity) of a specific event (as in mild, moderate, or severe myocardial infarction); however, the event itself may be of relatively minor medical significance (such as severe headache). This is not the same as "serious," which is based on subject/event outcome or action criteria usually associated with events that pose a threat to a subject's life or ability to function. Seriousness (not severity) serves as a guide for defining regulatory reporting obligations.

In general, the intensity of a particular AE to be recorded is the worst intensity experienced by the subject during the course of the event. The medical assessment of intensity will be determined by using the following definitions:

Mild: The AE is easily tolerated and does not interfere with usual activity.

Moderate: The AE interferes with daily activity, but the subject is still able to function.

Severe: The AE is incapacitating and the subject is unable to work or complete usual activity.

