## **10.3 Reporting Procedure for AEs, SAEs, and Pregnancy**

### **10.3.1 Adverse Events**

All AEs observed from time of signing of the ICF will be recorded in the subject's source documentation. This applies to all AEs regardless of presumed relationship to the study drug. For screen failure subjects, any AEs and SAEs occurring during the screening period (after informed consent) will be recorded in the subject's source documentation only and will not be collected on the eCRF. Adverse events leading to discontinuation of study drug must be collected.

If any AE is reported, the date of onset, relationship to study treatment, relationship to disease under study, any action taken, date of resolution (or the fact that it is still continuing or has become chronic), outcome, and whether the AE is serious or not, will be recorded. Use of colloquialisms and abbreviations should be avoided. Only one AE term should be recorded in the event field on the AE eCRF. Where possible, the Investigator should report a diagnosis rather than signs and symptoms or abnormal laboratory values. However, if a constellation of signs and/or symptoms cannot be medically characterized as a single diagnosis or syndrome at the time of reporting, each individual event should be recorded on the AE eCRF. If a diagnosis is subsequently established, all previously reported AEs based on signs and symptoms should be nullified and replaced by one AE report based on the single diagnosis, with a starting date that corresponds to the starting date of the first symptom of the eventual diagnosis.

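### The TEAE definition has no clause for adverse events that begin before first dose and worsen on voclosporin, so some non-serious events are left out of the TEAE summary

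*Combined protocol and SAP*

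**What the plan says.** Section 13.10 limits TEAEs by onset: "Only AEs which started on or after the date of first dose of study treatment and up until 14 days after last dose". The main adverse event table uses that set: "Treatment-emergent adverse events will be summarized by treatment arm, System Organ Class, and Preferred Term".

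The recording rules are elsewhere. Section 10.2.1 gives one grade per event: "the intensity of a particular AE to be recorded is the worst intensity experienced by the subject during the course of the event". Section 10.3.1 starts AE reporting at signature of the consent form. It lists the items to record for each event, including onset and resolution dates, and a date of worsening is not among them. When separate symptom records are later replaced by a diagnosis, the new record is entered "with a starting date that corresponds to the starting date of the first symptom of the eventual diagnosis". For the interval before dosing, footnote 12 of the Schedule of Events says: "Any change since the date of signed consent and/or during the screening period would be considered an AE".

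Section 13.10 also plans outputs that are not worded as TEAE-only: "SAEs, SAEs that led to death, and SAEs/AEs that led to withdrawal will also be summarized and listed", "SAEs occurring at any time after informed consent and prior to first study medication will be listed" and "Laboratory values, vital signs, and other safety parameters providing numeric data will be summarized by visit, and as change from baseline". The synopsis, under Safety Endpoints, describes AE tables by System Organ Class and preferred term with no TEAE restriction. Further detail is deferred to an SAP, and the file contains no SAP text on TEAEs.

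**The concern.** A start-date rule works when an event either begins on drug or has nothing to do with it. It fails for an event that is mild before dosing and gets worse on treatment, because the worsening is the part that matters for safety and the rule ignores it.

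Such events are plausible here. Section 1.2.4 names raised blood pressure as a known toxicity of calcineurin inhibitors. Appendix 1 provides for subjects who have hypertension at screening, and section 5.2 provides for treatment of nephrotic edema in the screening period. Safety and tolerability over 24 weeks is the only secondary objective (section 3.2). In a study of about 20 subjects, readers will look first at the TEAE table, and a term with one or two cases can appear in it or vanish on this rule alone.

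**Working it through.** The plan gives no figure to reproduce. The check follows one event through the rules and then sizes the effect of losing it.

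**Step 1: do pre-dose AEs exist in the data?** Yes. Reporting starts at consent (10.3.1). Screening lasts about 4 to 10 weeks (4.2), and consent may precede Visit 1 by up to 30 days (14.1).

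**Step 2: how is worsening recorded?** Take hypertension entered as a mild AE in screening that becomes severe in Week 6. Under 10.2.1 its single intensity becomes severe. Its start date stays in screening. No rule requires a second record or a worsening date.

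**Step 3: is it a TEAE?** No. Its start date precedes first dose, the 13.10 rule is exclusive, and no other section adds worsened events.

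**Step 4: where does it appear?**

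| Pre-dose AE that worsens on drug | Where it is reported |
|---|---|
| Becomes serious | SAE summary and listing (13.10) |
| Leads to withdrawal | Withdrawal summary and listing (13.10) |
| Laboratory abnormality | By-visit laboratory summaries; the worsening may itself count as an AE (10.2.4) |
| Confirmed eGFR fall above 30% | Its own secondary endpoint (13.8.2) |
| Blood pressure rise, non-serious, subject continues | By-visit vital signs; the event is absent from the TEAE table |
| Edema or another non-numeric event, non-serious, subject continues | Absent from the TEAE table, with no numeric summary of its own |

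The gap is the last two rows.

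**Step 5: size per masked subject.** If x of n subjects have a term and one is masked, incidence falls from x/n to (x − 1)/n, a change of 1/n. With the sample sizes in 13.2:

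- Overall: 1/20 = 5 percentage points.
- Cohort of 10: 1/10 = 10 percentage points.

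For scale, the exact (Clopper-Pearson) 95% intervals when a single case is lost are:

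| n | One case | No case |
|---|---|---|
| 10 | 0.3% to 44.5% | 0% to 30.8% |
| 20 | 0.1% to 24.9% | 0% to 16.8% |

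The intervals overlap heavily, so little precision is at stake. What changes is whether the term is shown at all.

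**Step 6: direction.** The missing clause can only exclude events, so it can only lower TEAE counts.

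**The case against.** The strongest reply is that the trial's main safety questions do not depend on this table. Renal toxicity has its own endpoint and change-from-baseline summaries. Blood pressure is summarized by visit. Serious events and AEs leading to withdrawal are reported separately. The study is descriptive, and 13.9 allows individual case reports. All of this stands, and it confines the point to one table.

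It does not remove the point. Section 1.2.4 reports that in lupus nephritis more TEAEs of hypertension occurred on voclosporin while mean blood pressure fell in every group. By-visit means can therefore miss what event counts show.

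Four stronger readings are tempting and are not supported:

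- **That these events drop out of the safety tables altogether.** They leave only the TEAE summary, and the unrestricted synopsis wording may even imply a table that includes them.
- **That disease present at entry is masked.** Under footnote 12, findings at a screening visit held on the day of consent are medical history. If such a condition first worsens on drug, that change can be a new AE with an on-treatment start.
- **That the back-dating rule sweeps in any worsening event.** It applies only when symptom records are replaced by a diagnosis.
- **That 13% to 35% of events are lost.** Those figures come from w/(w + 26), where w is the pre-dose weeks and 26 is 24 weeks plus 14 days: 4/30 = 13%, 10/36 = 28% and, with the 30-day consent interval added, 14.3/40.3 = 35%. They are shares of onset time under an assumed even onset rate. To be masked, an event must also persist to dosing, worsen, stay non-serious, not lead to withdrawal and not be re-entered.

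It is also fair to say that no rule forbids a new record on worsening and that the SAP may address this. But an SAP clause would contradict the exclusive wording of 13.10, and it could not be applied reliably if worsening dates were never collected.

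**Conclusion.** The point holds for one output. The TEAE summary by System Organ Class and preferred term omits AEs that begin between consent and first dose and worsen on treatment, when they are non-serious, do not lead to withdrawal and are not re-entered as new AEs. The number affected is unknown. The effect is 5 percentage points per masked subject overall and 10 in a cohort of 10, always downward, assuming the masked event is that subject's only occurrence of the term and the planned sample sizes are reached.

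The conclusion also assumes that sites follow the protocol as written and keep one record per event. AEs are among the data reviewed for the Cohort 2 dose decision (synopsis, Statistical Methods), but the documents do not say whether the TEAE rule governs that review, so no effect on that decision can be claimed. This is a modest defect that should be corrected because the correction is simple and the error runs one way.

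**What to change.** - **Definition (13.10).** Define a TEAE as an AE that starts on or after first dose, or that started earlier and increases in severity or becomes serious on or after first dose, in either case up to 14 days after last dose.
- **Data capture (10.2.1, 10.3.1 and the eCRF).** Record the worsening by one method only, to avoid double counting: either a worsening date and grade on the existing record, or a new record dated at the worsening. Keep that date if symptom records are later replaced by a diagnosis.
- **Consistency.** Align the synopsis, which describes tables of all AEs, with 13.10, which describes tables of TEAEs. Carry the same definition into the SAP.

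The cost is a few sentences of text, a small eCRF change and a completion note for sites. Reported TEAE rates may rise slightly. The change should come as early as possible: the definition can be amended at any time before database lock, but worsening dates that were not collected may be hard to recover.
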